8.2 ADVERSE EVENTS AND SERIOUS ADVERSE EVENTS

8.2.1 DEFINITION OF ADVERSE EVENTS (AE)

Adverse event means any untoward medical occurrence associated with the use of an intervention (Galnobax® plus SoC or only SoC or Vehicle plus SoC) in humans, whether or not considered intervention-related.

8.2.2 DEFINITION OF SERIOUS ADVERSE EVENTS (SAE)

An adverse event (AE) or suspected adverse reaction is considered "serious" if, in the view of either the Investigator or the Sponsor, it results in any of the following outcomes: death, a life-threatening adverse event, inpatient hospitalization, a persistent or significant incapacity or substantial disruption of the ability to conduct normal life functions.

8.2.3 CLASSIFICATION OF AN ADVERSE EVENT

8.2.3.1 SEVERITY OF EVENT

The intensity of all AEs occurring during the course of the Study will be graded according to NCI-CTCAE, version 4.0. as provided in Table 5:

Table 5 Assessment of Intensity

Grade	Description of Intensity Grading
1	Mild
2	Moderate
3	Severe
4	Life-threatening or disabling
5	Death

8.2.3.2 RELATIONSHIP TO STUDY INTERVENTION

Every effort would be made by the Investigator to explain each AE and assess its causal relationship, if any, to application of the IP.

Causality of all AEs would be assessed by the Investigator depending upon various factors like the temporal relationship of the AE to Study IP application, whether AE follows a known pattern of response to IP, any other cause to which the AE can be attributed or intensity of AE changes.

Relationship of AEs to Study treatment will be classified as follows:

1. Unrelated – The event is definitely not associated with the Study drug. Other conditions including concurrent illness, progression or expression of the disease state, or reaction to a concurrent medication explain the reported AE.
2. Unlikely – The temporal association, Subject history and/or circumstances are such that the Study drug is not likely to have had an association with the observed event. Other conditions including concurrent illness, progression or expression of the disease state, or reaction to a concurrent medication, appear to explain the reported AE.
3. Possibly – The event follows a reasonable temporal sequence from Study drug but could have been produced by the Subject's clinical state or other therapies administered to the Subject.
4. Probably – The event follows a reasonable temporal sequence from the Study drug, abates upon discontinuation of the Study drug or control, and cannot be reasonably explained by known characteristics of the Subject's clinical state.
5. Definitely – The event follows a reasonable temporal sequence from the Study drug, abates upon discontinuation or cannot be explained by known characteristics of the Subject's clinical state.

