6.5 CONCOMITANT THERAPY

Any medication regularly used by the Subject including anti-diabetic medications as prescribed by the physician and approved by the Investigator will be permitted to be used.

If Investigator suspects infection at any wound site of the Subject, oral and/or parenteral antibiotics (except topical) and standard of wound care will be permissible to prevent the wound from leading to osteomyelitis. It will be at the Investigator's discretion to decide if it is necessary to defer the Study treatment to the Subject during the antibiotic treatment to control the wound infection. In case the non-Study ulcer is seen with infection, it will be treated with oral or parenteral antibiotics. The local antimicrobial therapy, if required will be permitted to the non-Study ulcer.

The concomitant medication administered must also be recorded in the CRF with generic name and/or trade name of the medication, dose, start and end dates of treatment.

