8.2.12 EXPEDITED SAFETY REPORTING

Any serious AE, which is unexpected and at least possibly related to the IP calls for expedited reporting to the regulatory authorities and the ECs as per CDSCO requirements.

As the CRO acts on behalf of the Sponsor, the regulatory reporting time clock starts when any member of the CRO safety team qualifies a SAE as an expedited SAE, in consultation with the Sponsor.

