9.4.4.1 TREATMENT EMERGENT ADVERSE EVENT

Treatment emergent adverse events (TEAE) are undesirable events not present prior to medical treatment, or an already present event that worsens either in intensity or frequency following the treatment. The TEAEs, which is defined as all AEs on or after the application of first dose of IP will be summarized according to the numbers and percentages of TEAEs as well as numbers and percentages of Subjects with one or more occurrences of TEAEs during the Study. Number of Subjects with TEAEs and number of events of TEAEs will be tabulated by preferred term (PT) and system organ class (SOCL). If a Subject had more than one TEAE, event will be counted only once in SOCL and once for each PT.

Summaries of TEAEs by severity grade, relationship to Study medication, leading to death, SAEs of study, IP related TEAEs will be provided.

Also, summarization for SAE, SAEs by severity, SAEs by relationship to Study IP will be provided separately.

Listing will be provided for all Subjects who have at least one adverse event.

AEs will be coded using the MedDRA, version 20.0 or later.

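### In section 8.2.3.2 the causality grade Definitely has a weaker test than Probably, so the relatedness categories are out of order and overlap

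*Combined protocol and SAP*

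**What the plan says.** Protocol section 8.2.3.2 has the Investigator place each adverse event in one of five categories: *Unrelated*, *Unlikely*, *Possibly*, *Probably*, *Definitely*. The top three all start from a reasonable temporal sequence. They then differ:

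- *Possibly*: the sequence fits, "but could have been produced by the Subject's clinical state or other therapies administered to the Subject".
- *Probably*: the event "abates upon discontinuation of the Study drug or control, and cannot be reasonably explained by known characteristics of the Subject's clinical state".
- *Definitely*: the event "abates upon discontinuation or cannot be explained by known characteristics of the Subject's clinical state".

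*Definitely* carries no further condition, such as recurrence on re-application or a known response pattern. No other section redefines the categories, and none says what to do when an event fits more than one.

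The grade is used in section 9.4.4.1: "Summaries of TEAEs by severity grade, relationship to Study medication, leading to death, SAEs of study, IP related TEAEs will be provided". The same section tabulates SAEs by relationship. Section 8.2.12 uses it as a threshold: "Any serious AE, which is unexpected and at least possibly related to the IP calls for expedited reporting".

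**The concern.** A causality scale should ask for more evidence as the label gets stronger. Here the link between the last two conditions is 'and' for *Probably* and 'or' for *Definitely*. An event with only one of the two pieces of evidence fails *Probably* but passes *Definitely*.

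The situation can plausibly arise. Section 6.5 leaves it to the Investigator to "decide if it is necessary to defer the Study treatment to the Subject during the antibiotic treatment", and section 8.2.3.3 requires infection at the ulcer to be reported as an AE. In addition, treatment ends for every Subject at closure or week 12, and AEs are then recorded through a 12-week follow-up. An event that starts on treatment, has an evident cause in the underlying disease and settles after treatment stops can be read as having abated on discontinuation.

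At stake is the meaning of the by-relationship tables. Section 9.4.4 plans no formal testing of safety, so those tables are read at face value. Events explained by the disease could sit under the strongest label, and *Probably* would have no content of its own.

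**Working it through.** The plan gives no figure to reproduce. The check is a truth table over the definitions in 8.2.3.2.

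**Inputs.** T = reasonable temporal sequence. A = abates on discontinuation. R = explanation by the clinical state: 0 none, 1 some but not reasonable, 2 reasonable. R needs three levels because *Probably* excludes only a reasonable explanation, while *Definitely*, in its second limb, excludes any explanation.

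**Rules as written.**
- *Possibly* = T and R ≥ 1
- *Probably* = T and A and R < 2
- *Definitely* = T and (A or R = 0)

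**Rule with 'or' replaced by 'and'.**
- *Definitely* = T and A and R = 0

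**Results for the 2 × 3 = 6 patterns with T present.**

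| A | R | Possibly | Probably | Definitely, as written | Definitely, with 'and' |
|---|---|---|---|---|---|
| yes | 0 | no | yes | yes | yes |
| yes | 1 | yes | yes | yes | no |
| yes | 2 | yes | no | yes | no |
| no | 0 | no | no | yes | no |
| no | 1 | yes | no | no | no |
| no | 2 | yes | no | no | no |

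1. As written, *Definitely* is met in 4 of 6 patterns and *Probably* in 2 of 6. Both *Probably* patterns also meet *Definitely*.
2. Two patterns meet *Definitely* but fail *Probably*. One abates and is reasonably explained (row 3), and it also meets *Possibly*. The other does not abate and is unexplained (row 4).
3. Collapsing R to explained or not explained gives 3 of 4 against 1 of 4, with the same nesting.
4. If the loosely punctuated *Definitely* text is read as any one of three conditions, it is met in 10 of all 12 patterns (T present or absent), so that reading is wider still.
5. With 'and', *Definitely* is met in 1 of 6 patterns and lies inside the 2 of 6 that meet *Probably*. No event explained by the clinical state meets it.

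**Effect on the tables.** Section 9.4.4.1 does not say which grades count as IP related. If the group is *Possibly* and above, coding a row 3 event *Possibly* or *Definitely* leaves the IP-related count unchanged and alters only the split by grade. If the group starts at *Probably*, or is *Definitely* alone, the choice moves the event into or out of the count.

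**The case against.** The fairest reply is that this is a one-word slip inside a judgement-based scale. Section 8.2.3.2 also tells the Investigator to weigh timing, known response patterns and other possible causes, and a sensible Investigator would not call an explained event *Definitely* related. The second limb of *Definitely* is also slightly stricter, since it drops the word 'reasonably'. The first part stands this far: the text permits miscoding but does not make it certain. The second does not restore the order, because abatement alone satisfies the 'or'.

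Several stronger readings are tempting, and the documents do not support them:

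- **That expedited reporting changes.** The trigger in 8.2.12 starts at *Possibly*, so moves among the three upper grades leave it where it is. The event must also be serious and unexpected, and 8.2.3.3 already names wound infection as something that cannot be ruled out.
- **That one event can properly be coded *Unlikely* or *Definitely*.** *Unlikely* rests on a judgement that the drug probably had no association with the event. The overlap arises only if the instruction to weigh other causes is ignored. The firm overlap is *Possibly* with *Definitely*.
- **That follow-up after withdrawal depends on the grade.** Section 7.2 mentions related events, but 8.2.4 follows all AEs to resolution, and 8.2.6 follows those open at exit without a relatedness condition.
- **That the related count would multiply, given 2 related AEs of 29 in Phase 1/2.** The documents give no infection or deferral rate for this trial, nor the causality scale used in Phase 1/2.
- **That every treated infection is an example.** Section 6.5 speaks of deferring treatment, not discontinuing it, and some infections lead to discontinuation from the Study under 7.2.

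**Conclusion.** The definitions are wrong as written. *Definitely* has a weaker test than *Probably*, *Probably* is never the only label that fits, and an event that abates but is explained by the clinical state can be coded *Possibly* or *Definitely*.

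The effect is confined to the TEAE and SAE summaries by relationship and, depending on an unstated grouping, to the IP-related TEAE table. The primary endpoint does not use the scale. Nor does the safety endpoint, which counts Subjects with TEAEs whatever their relationship. One scale serves all arms and the assessing Investigator is blinded, so no bias between arms is shown.

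The figures 4 of 6 and 2 of 6 count logical patterns, not expected events; the documents give no basis for a frequency. They assume the definitions are applied literally and that explanation means explanation by the clinical state, as in the top two definitions. *Possibly* also admits other therapies, which the table does not model separately.

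**What to change.** In 8.2.3.2, in the *Definitely* definition, replace the 'or' between the abatement clause and the explanation clause with 'and'. Add one sentence: an event takes the highest category whose criteria are all met. The two edits belong together, because under the present 'or' a highest-match rule would send every *Probably* event to *Definitely*. No extra condition for *Definitely* is needed to restore the order. A rule that stops at the lowest match should be avoided, since it could make the top category impossible to assign.

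The edit leaves one gap. An event in temporal sequence that does not abate and has no explanation (row 4) now meets only *Definitely*, and would then meet none of the top three unless another therapy could account for it. The sponsor should state which category it takes.

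Update the eCRF completion guide to match. The cost is one word, a sentence or two and the guide. No new data, visits or rechallenge are needed. The change is best made before events are coded, because a later change would mean asking Investigators to reassess them.

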8.2.3.3 EXPECTEDNESS

Investigator will be responsible for determining whether an adverse event (AE) is expected or unexpected. An AE will be considered unexpected if the nature, severity, or frequency of the event is not consistent with the risk information available for the study intervention. The treatment is being given topically in this Study, therefore the AEs that are expected at and around the Target Ulcer location are: hypersensitivity, irritation, inflammation of ulcer. Since the Target Ulcer is an open wound, possibility of infection at the wound site cannot be ruled out. The infection at Target or non-Target Ulcer will be reported as AE.

8.2.4 TIME PERIOD AND FREQUENCY FOR EVENT ASSESSMENT AND FOLLOW-UP

The occurrence of an adverse event (AE) or serious adverse event (SAE) may come to the attention of Study personnel during Study visits or Study Nurse during visits to Subject and interviews of a Study Subject presenting for medical care, or upon review by a study monitor.

All AEs including local and systemic reactions not meeting the criteria for SAEs will be captured on the appropriate electronic case report form (eCRF). Information to be collected includes duration (start and end dates), severity/intensity, relationship to IP, specific therapy, results and consequences and seriousness. All AEs occurring while on Study must be documented appropriately regardless of relationship. All AEs will be followed to adequate resolution.

Any medical condition that is present at the time that the participant is screened or before application of first dose will be considered as baseline and not reported as an AE. However, if the Study participant's condition deteriorates at any time during the study, it will be recorded as an AE.

Changes in the severity of an AE will be documented to allow an assessment of the duration of the event at each level of severity to be performed. AEs characterized as intermittent require documentation of onset and duration of each episode.

The Investigator will record all reportable events with start dates occurring any time after informed consent is obtained till the last day of Study participation. At each Study visit, the Investigator will inquire about the occurrence of AE/SAEs since the last visit. Events will be followed for outcome information until resolution or stabilization. An AE can reach one of the following outcomes:

- a. Complete recovery (AE/ SAE end date will be captured).
- b. Recovered with sequelae. (AE/ SAE end date will be captured and the sequelae will be specified).
- c. Ongoing
- d. Death
- e. Unknown: The outcome of the event may be captured as unknown only in the exceptional cases when the Subject is lost to follow-up (AE end date will be left blank).

8.2.5 ADVERSE EVENT REPORTING

AEs will be assessed during each visit by doing clinical examination, review of the laboratory investigations and by directly questioning the Subject/LAR/impartial witness. The increase of Target Ulcer size or its worsening will be considered as adverse event. The change from Baseline in laboratory values, vital signs and ECG/EKG parameters outside accepted or normal range will be reported as adverse event irrespective of Investigator's opinion on clinical significance of such abnormality.

As far as possible each AE should be described to include:

- Duration (start and end dates)
- Severity/Intensity
- Relationship to IP or Specific therapy
- Results and Consequences
- Seriousness

Those AEs that are already documented in the CRFs, at a previous assessment and designated as 'ongoing' would be reviewed at subsequent visits, as necessary. If these have resolved, the documentation in the CRF would be completed.

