Endpoints:	
Primary Endpoint:
 
Efficacy endpoint: The efficacy assessment will involve Galnobax® plus Standard of Care and only Standard of Care groups
 
 1. Proportion of Subjects achieving Target Ulcer Closure within 12-week Treatment Phase, as assessed by blinded Investigator. 
Secondary Endpoints:
 
Efficacy endpoints:
 
 1. Time to Target Ulcer Closure during the 12-week Treatment Phase, as assessed by the blinded Investigator. 2. Proportion of Subjects achieving Target Ulcer Closure till End of Study, as assessed by the blinded Investigator. 
Safety endpoints:
 
 1. Proportion of Subjects with treatment emergent adverse events (TEAEs). 2. Proportion of Subjects with events related to the local wound assessment of Target Ulcer in Vehicle plus Standard of Care group.
Study Population:	
A maximum of 350 Subjects will be randomized for this Phase 3 clinical Study who have DFU and satisfy eligibility criteria given below and in Section 5. The break-up of these 350 Subjects is as follows:
 
Group 1: Galnobax® + SoC such that minimum number of Subjects in this group is 120.
 
Group 2: SoC alone such that minimum number of Subjects in this group is 120.
 
Provision for drop-outs in Groups 1 and 2: 20% i.e. 60 Subjects
 
Group 3: Vehicle + SoC such that the maximum number of Subjects in this group is 50 to evaluate the safety of Galnobax® vehicle.
 
Eligibility Criteria
 
a. Inclusion criteria
 
The Subjects who satisfy all the following inclusion criteria will be enrolled in the Study and subsequently randomized:

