Target Ulcer classification and its measurement: Classification of all the potential Target Ulcers and its measurement will be completed as per Texas system at the screening visit (V1). The classification and measurement will be done for selected Target Ulcer at Baseline Visit (V2) as well as in all Treatment and Follow-up Visits (V3 to V18) (See Attachment 1). The measurement of the Target Ulcer area will be done using advance camera. The parameters captured will be area, volume, mean depth and maximal depth. It should however be noted that volume and depth measurements may be inaccurate to the extent of the advance camera's technical limitations. In the event of inability to measure wound size by advance camera, the Target Ulcer area measurement will be done with the help of wound tracing in conjunction with planimetry software. In such situation, only Target Ulcer area will be measured.

Target Ulcer characteristics: Assessment of Target Ulcer characteristics in terms of wound edge, color, drainage amount and type, peri-wound conditions and color and percent wound bed covered by granulation tissue, fibrin slough, and necrotic tissue will be done at all Visits (V1 to V18).

Wound Care: Wound care to be taken during the Study will be explained to the Subject by the Investigator at the time of Screening and periodically. This will include following:

1. A moist wound environment as suitable for the condition of wound (moist bandage should not be used in case wound is oozing and highly moist)
2. Non-adherence of dressing to the wound
3. Allowance for removal of dressing from the wound without pain or trauma
4. Role of the dressing to absorb the excess wound exudates
5. Allowance for gaseous exchange through the protective dressing
6. Prevent permeance to microorganisms

Debridement of Target Ulcer: Debridement of the Target Ulcer, if required along with documentation of type of debridement (e.g. callus removal, sharp or surgical), reason for debridement will be recorded at Screening Visit V1 and all treatment and Follow-up visits V2 to V18 (as and when necessary).

The Target Ulcer will be surgically debrided, if required as per procedure given below.

1. Perform sharp debridement to remove all necrotic soft tissue, hyperkeratotic wound margins, bacterial burden, cellular debris, sinus tracts, fistulae, undermined borders, and callus to produce viable wound margins and a clean ulcer site.

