8.2.7 EVENT NOT TO REPORTED AS AE

Progression of underlying disease (at Investigator's discretion) / Study indication/lack of efficacy of the IP would NOT be reported as an AE/SAE.

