8.2.8 SERIOUS ADVERSE EVENT REPORTING

- Any SAE occurring during the course of the Study would be treated by established standards of care to protect the life and health of the Subject
- Any SAE, irrespective of causality, must be immediately notified to the safety team at the CRO and the Sponsor. It must be followed up within 24 hours on the Study specific SAE reporting form with as much detailed information regarding the event that is available
- Investigators would not wait to receive additional information to fully document the event, before notifying SAE to the CRO.
- The SAE reporting form should detail all relevant aspects of the AEs in question. Where applicable, information from relevant hospital case records and autopsy reports would be obtained and provided, in a blinded fashion, to the CRO.
- All SAEs would be reported within 24 hours of Investigator's knowledge of the event to the CRO. and to the respective EC and Regulatory authorities (CDSCO) by the Investigator as soon as possible as per applicable regulations. The Investigator site and the sponsor would have to copy all SAE related communications on [contact] while communicating with the CRO and [contact] for communicating with the Sponsor. The SAE forms should be shared via E-mail as scanned attachments
- The event must also be recorded on the CRF AE page
- The follow up SAE form also should be filled and sent to the CRO, the Sponsor, CDSCO and EC within 24 hours of updated information on SAE
- Communicate filled CIOMS-I MedWatch form within 14 calendar days to CDSCO

The CRO does not prefer Fax as the mode of communication for SAEs. However, if a site would insist on using fax then the site should have to send an email stating the information that the fax has been sent. In the event of any technical issue wherein the site would not be able to send the

Email, then a phone call should be made to the concerned medical monitor to inform that SAE form sent via fax.

Fax: [name]

All the events will be monitored by the Investigator until the event has subsided or, in a case of permanent impairment, until the event stabilizes and the overall clinical outcome has been ascertained.

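### Sections 8.2.5 and 8.2.7 give opposite reporting rules for a non-infected, worsening Target Ulcer, and nothing says which prevails

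*Combined protocol and SAP*

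**What the plan says.** Three places in the protocol treat worsening as recordable.

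- Section 8.2.5 names the Target Ulcer: "The increase of Target Ulcer size or its worsening will be considered as adverse event". It gives no size threshold, no reference visit and no exception.
- Section 8.2.4, in general terms, covers any condition present before the first dose: if the participant's "condition deteriorates at any time during the study, it will be recorded as an AE".
- Section 9.4.4.1 counts as treatment emergent an event already present that worsens after treatment. It then gives the working definition of TEAEs, "which is defined as all AEs on or after the application of first dose of IP".

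Section 8.2.7 points the other way. It lists progression of the underlying disease (at the Investigator's discretion), the study indication, and finally "lack of efficacy of the IP would NOT be reported as an AE/SAE".

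The proportion of Subjects with TEAEs is the first safety endpoint in Section 1.1. It is analysed descriptively in the ITT (safety) population (9.4.1, 9.4.4). The serious outcomes in Section 8.2.2 include "death, a life-threatening adverse event, inpatient hospitalization". Section 8.2.8 says: "Any SAE, irrespective of causality, must be immediately notified to the safety team at the CRO and the Sponsor".

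**The concern.** The study indication is the diabetic foot ulcer, and each Subject has one Target Ulcer. Its enlargement is therefore both the event that 8.2.5 names and, on a plain reading, the progression that 8.2.7 exempts. The same event is recorded at a site that follows the first rule and omitted at a site that follows the second.

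Two outputs are exposed. The first is the TEAE proportion, which takes over whatever the AE rule admits. The second is SAE notification: a hospitalization for non-infected ulcer progression is reported under one rule and exempt under the other. Whether treatment or Vehicle harms healing is one of the trial's safety questions (Sections 1.1 and 4.2), and ulcer worsening is the form such harm would most directly take.

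**Working it through.** **Text comparison**

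| Event at the Target Ulcer | Under 8.2.4 / 8.2.5 | Under 8.2.7 | Conflict? |
|---|---|---|---|
| Infection | AE (also named in 8.2.3.3) | AE, because 8.2.3.3 names it | No |
| Enlargement or worsening, no infection | AE | Not an AE if read as progression or lack of efficacy | Yes |
| Hospitalization for non-infected progression | SAE, notified under 8.2.8 | Not an SAE | Yes |

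No section ranks the rules, and 8.2.7 contains no exception for the Target Ulcer. The protocol's one threshold for ulcer growth during treatment, more than 30% for two consecutive weeks (Section 7.2), is a discontinuation rule and does not define an AE.

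**Illustration of size**

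The plan states no figure to reproduce and gives no worsening rates. What follows shows only how the size would behave under assumptions.

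Assumed quantities:
- f: share of non-closers with a recorded worsening
- g: share of closers with a recorded worsening
- b: share of Subjects with another TEAE, equal in both arms and independent of worsening

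Closure rates: Section 9.2 plans 39% (SoC) and 60% (Galnobax), but for the FAS. TEAEs are analysed in the ITT population. If the planned 20% drop-outs are all dosed non-closers, ITT closure is 0.80 × 39 = 31.2% and 0.80 × 60 = 48.0%. Non-closers are then 68.8% and 52.0%.

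Points added to the TEAE proportion when worsening is recorded as an AE:
- SoC: (1 − b)(68.8f + 31.2g)
- Galnobax: (1 − b)(52.0f + 48.0g)
- Difference: 16.8(f − g)(1 − b)

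Each cell gives SoC / Galnobax / difference, in percentage points:

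| f, g | b = 0 | b = 0.3 | b = 0.6 | b = 0.9 |
|---|---|---|---|---|
| 0.25, 0.25 | 25.0 / 25.0 / 0 | 17.5 / 17.5 / 0 | 10.0 / 10.0 / 0 | 2.5 / 2.5 / 0 |
| 0.50, 0.25 | 42.2 / 38.0 / 4.2 | 29.5 / 26.6 / 2.9 | 16.9 / 15.2 / 1.7 | 4.2 / 3.8 / 0.4 |
| 0.75, 0 | 51.6 / 39.0 / 12.6 | 36.1 / 27.3 / 8.8 | 20.6 / 15.6 / 5.0 | 5.2 / 3.9 / 1.3 |

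Using the FAS rates unadjusted would make the multiplier 60 − 39 = 21 and the largest difference 21 × 0.75 = 15.8 points. That is the wrong population for this endpoint.

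If only a share s of Subjects is at sites that follow 8.2.5, and s is the same in both arms, every entry is multiplied by s.

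The right-hand columns deserve weight. Section 8.2.5 also makes laboratory, vital-sign and ECG changes outside the normal range AEs whatever the Investigator thinks of their clinical significance. In a diabetic population with frequent testing this may push b high.

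**The case against.** The strongest reply is that the specific rule governs the general one. Section 8.2.5 names Target Ulcer size, 8.2.4 and 9.4.4.1 agree with it, and 8.2.7 is one generic sentence that never mentions the Target Ulcer. Lack of efficacy can also be read as failure to close rather than growth. This is a natural reading, but the protocol does not state it. Section 8.2.7 can equally be read as the exception to the rules before it. Progression of the study indication still describes an enlarging ulcer, and the stated discretion lets sites differ in good faith.

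A second reply is that little is lost, because "measurement will be done for selected Target Ulcer at Baseline Visit (V2) as well as in all Treatment and Follow-up Visits". That largely stands for size: enlargement at attended visits can be derived later, and infection status and ulcer characteristics are recorded as well. After discontinuation, however, Section 7.2 asks the Subject to cooperate only with AE recording and follow-up. A judgment of causality and seriousness made at the time, and prompt SAE notification, cannot be rebuilt from areas. The separate SAP promised in 9.4.1 cannot recover events that sites never recorded.

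A third reply limits the SAE consequence, and it is right. Under 8.2.2 a hospitalization is serious only if the event is first an AE, and infection is an AE under either rule. A reader might infer that serious ulcer events in general would go unreported. The documents support this only for non-infected progression, at sites that apply 8.2.7.

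The independence assumption also favours larger figures. If worsening ulcers are more often infected, many of those Subjects already have a TEAE and the added share is smaller than shown.

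**Conclusion.** The contradiction stands: two explicit rules cover a non-infected, worsening Target Ulcer and give opposite instructions. It should be corrected, because the first-listed safety endpoint has no single meaning across about 40 sites until it is, and one class of possible SAE is captured or missed by site interpretation.

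The size is not known. The illustrated between-arm difference of 0 to 12.6 points rests on assumed worsening rates, on all drop-outs being dosed non-closers, and on independence and equal b. It is zero whenever closers and non-closers worsen equally often, and small when most Subjects have another TEAE.

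A reader might infer that the TEAE comparison is bound to favour Galnobax by a sizeable margin. Without worsening rates the documents do not support that. The Investigator is also blinded (Section 6.3), which limits any choice of rule by arm.

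Nor is the clinical-significance wording in Sections 8.1 and 9.4.4.2 a further contradiction. It is narrower than the out-of-range rule in 8.2.5 but does not oppose it.

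The safety analysis is descriptive. The primary test, alpha and sample size are unaffected.

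**What to change.** Reconcile 8.2.4, 8.2.5 and 8.2.7 into one recording rule for all arms and sites. State, separately for AEs and for SAEs, whether the 8.2.7 exemption covers the Target Ulcer, and say which visit an increase is measured against. Which rule to adopt is for the sponsor to decide.

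Add two descriptive outputs:
- Target Ulcer enlargement by arm, derived from the areas already measured at each visit. Include the Vehicle arm, because the Vehicle table planned in Section 9.4.4 names only local pain, edema and erythema.
- The TEAE proportion with and without Target Ulcer worsening.

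The cost is protocol and CRF-guideline wording, a few table lines, and possibly more AE entries at sites that would otherwise have applied 8.2.7.
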